6.2.7 Non-Target Lesions

All other lesions (or sites of disease) including any measurable lesions over and above the 5 target lesions should be identified as **non-target lesions** and should also be recorded at baseline. Measurements of these lesions are not required, but the presence, absence, or in rare cases unequivocal progression of each should be noted throughout follow-up.

6.2.8 Metastatic Bone Lesions

Disease progression is considered if a minimum of two new lesions is observed on bone scan. New lesions seen by the end of cycle 2 or before cycle 3 (with the first re-staging bone scan) may represent disease that was not detected on the pre-study scan, and a confirmatory scan will be required at the next scheduled re-staging bone scan unless clinically not indicated. If confirmed, progression should be dated by the initial time when the lesions are first detected. If new lesions are seen after cycle 2, but no additional lesions are seen on confirmatory scans, the scans from post-cycle 2 would serve as the baseline scan to evaluate for disease progression (49).

Clinical Lesions

Clinical lesions will only be considered measurable when they are superficial (e.g., skin nodules and palpable lymph nodes) and ≥ 10 mm diameter as assessed using calipers (e.g., skin nodules). In the case of skin lesions, documentation by color photography, including a ruler to estimate the size of the lesion, is recommended.

6.2.9 Guidelines for Evaluation of Measurable Disease

All measurements should be taken and recorded in metric notation using a ruler or calipers. All baseline evaluations should be performed as closely as possible to the beginning of treatment and never more than 4 weeks before the beginning of the treatment.

The same method of assessment and the same technique should be used to characterize each identified and reported lesion at baseline and during follow-up. Imaging-based evaluation is preferred to evaluation by clinical examination unless the lesion(s) being followed cannot be imaged but are assessable by clinical exam.

6.2.10 Methods of Measurement

Chest X-ray - Lesions on chest x-ray are acceptable as measurable lesions when they are clearly defined and surrounded by aerated lung. However, CT is preferable.

CT and MRI - CT and MRI are the best currently available and reproducible methods to measure target lesions selected for response assessment. For this study helical Multi-detector CT will be performed with cuts of 5 mm in slice thickness for chest, abdomen and pelvis lesions and 2-3 mm thickness for head and neck lesions.

6.2.11 Additional response evaluation using volumetric analysis

In addition, the utility of volumetric tumor measurement in patients with measurable disease will be prospectively evaluated and compared to 1D and 2D measurements. All sites will submit baseline and restaging studies to NCI for volumetric analysis. (See [Error! Reference source not found.](#) for details).

6.3 TOXICITY CRITERIA

The following adverse event management guidelines are intended to ensure the safety of each patient while on the study. The descriptions and grading scales found in the revised NCI Common Terminology Criteria for Adverse Events (CTCAE) version 4.0 will be utilized for AE reporting. All appropriate treatment areas have access to a copy of the CTCAE version 4.0. A copy of the CTCAE version 4.0 can be downloaded from the CTEP web site (<http://ctep.cancer.gov>).

7 SAFETY REPORTING REQUIREMENTS/DATA AND SAFETY MONITORING PLAN

7.1 DEFINITIONS

7.1.1 Adverse Event

An adverse event is defined as any reaction, side effect, or untoward event that occurs during the course of the clinical trial, whether or not the event is considered related to the treatment or clinically significant. For this study, AEs will include events reported by the patient, as well as clinically significant abnormal findings on physical examination or laboratory evaluation. A new illness, symptom, sign or clinically significant laboratory abnormality or worsening of a pre-existing condition or abnormality is considered an AE. All AEs must be recorded on the AE case report form.

All AEs, including clinically significant abnormal findings on laboratory evaluations, regardless of severity, will be followed until satisfactory resolution. AEs should be reported up to 30 days after the last administration of investigational agent/intervention and have an attribution of at least possibly related to the agent/intervention should be recorded and reported as per sections [7.2](#), [7.3](#), and [7.4](#).

An abnormal laboratory value will be considered an AE if the laboratory abnormality is characterized by any of the following:

- Results in discontinuation from the study
- Is associated with clinical signs or symptoms
- Requires treatment or any other therapeutic intervention
- Is associated with death or another serious adverse event, including hospitalization
- Is judged by the Investigator to be of significant clinical impact
- If any abnormal laboratory result is considered clinically significant, the investigator will provide details about the action taken with respect to the test drug and about the patient's outcome.

7.1.2 Suspected adverse reaction

Suspected adverse reaction means any adverse event for which there is a reasonable possibility that the drug caused the adverse event. For the purposes of IND safety reporting, 'reasonable

possibility' means there is evidence to suggest a causal relationship between the drug and the adverse event. A suspected adverse reaction implies a lesser degree of certainty about causality than adverse reaction, which means any adverse event caused by a drug.

7.1.3 Unexpected adverse reaction

An adverse event or suspected adverse reaction is considered "unexpected" if it is not listed in the investigator brochure or is not listed at the specificity or severity that has been observed; or, if an investigator brochure is not required or available, is not consistent with the risk information described in the general investigational plan or elsewhere in the current application. "Unexpected", also refers to adverse events or suspected adverse reactions that are mentioned in the investigator brochure as occurring with a class of drugs or as anticipated from the pharmacological properties of the drug, but are not specifically mentioned as occurring with the particular drug under investigation.

7.1.4 Serious

An Unanticipated Problem or Protocol Deviation is serious if it meets the definition of a Serious Adverse Event or if it compromises the safety, welfare or rights of subjects or others.

7.1.5 Serious Adverse Event (SAE)

An adverse event or suspected adverse reaction is considered serious if in the view of the investigator or the sponsor, it results in any of the following:

- Death
- A life-threatening adverse drug experience
- Inpatient hospitalization or prolongation of existing hospitalization
- Persistent or significant incapacity or substantial disruption of the ability to conduct normal life functions
- A congenital anomaly/birth defect
- Important medical events that may not result in death, be life-threatening, or require hospitalization may be considered a serious adverse drug experience when, based upon appropriate medical judgment, they may jeopardize the patient or subject and may require medical or surgical intervention to prevent one of the outcomes listed in this definition

7.1.6 Disability

A substantial disruption of a person's ability to conduct normal life functions.

7.1.7 Life-threatening adverse drug experience

Any adverse event or suspected adverse reaction that places the patient or subject, in the view of the investigator or sponsor, at immediate risk of death from the reaction as it occurred, i.e., it does not include a reaction that had it occurred in a more severe form, might have caused death.

7.1.8 Protocol Deviation (NIH Definition)

Any change, divergence, or departure from the IRB approved research protocol.

7.1.9 Non-Compliance (NIH Definition)

The failure to comply with applicable NIH Human Research Protections Program (HRPP) policies, IRB requirements, or regulatory requirements for the protection of human research subjects.

7.1.10 Unanticipated Problem

Any incident, experience, or outcome that:

- Is unexpected in terms of nature, severity, or frequency in relation to
 - (a) the research risks that are described in the IRB-approved research protocol and informed consent document; Investigator's Brochure or other study documents, and
 - (b) the characteristics of the subject population being studied; **AND**
- Is related or possibly related to participation in the research; **AND**
- Suggests that the research places subjects or others at a *greater risk of harm* (including physical, psychological, economic, or social harm) than was previously known or recognized.

7.2 NCI-IRB AND NCI CLINICAL DIRECTOR REPORTING

7.2.1 NCI-IRB and NCI CD Expedited Reporting of Unanticipated Problems and Deaths

The Protocol PI will report in the NIH Problem Form to the NCI-IRB and NCI Clinical Director:

- All deaths, except deaths due to progressive disease
- All Protocol Deviations
- All Unanticipated Problems
- All non-compliance

Reports must be received within 7 working days of PI awareness via iRIS.

7.2.2 NCI-IRB Requirements for PI Reporting at Continuing Review

The protocol PI will report to the NCI-IRB:

1. A summary of all protocol deviations in a tabular format to include the date the deviation occurred, a brief description of the deviation and any corrective action.
2. A summary of any instances of non-compliance
3. A tabular summary of the following adverse events:
 - All Grade 2 **unexpected** events that are possibly, probably or definitely related to the research;
 - All Grade 3 and 4 events that are possibly, probably or definitely related to the research;
 - All Grade 5 events regardless of attribution;
 - All Serious Events regardless of attribution.

NOTE: Grade 1 events are not required to be reported.

7.2.3 NCI-IRB Reporting of IND Safety Reports

Only IND Safety Reports that meet the definition of an unanticipated problem will need to be reported to the NCI IRB.

7.2.4 Request for waiver from IRB reporting: Anticipated PD and Expedited Non-UP AEs

Protocol evaluations and initiation of mithramycin treatment for subsequent cycles, which are performed within a window of +/- 7 days of the protocol required schedule will not be considered a deviation, and not reported to the IRB.

7.3 IND SPONSOR REPORTING CRITERIA

7.3.1 Expedited Adverse Event Reporting Criteria to the IND Sponsor

An investigator must immediately report to the sponsor, using the mandatory MedWatch form 3500a, any serious adverse event, whether or not considered drug related, including those listed in the protocol or investigator brochure and must include an assessment of whether there is a reasonable possibility that the drug caused the event.

- All Grade 5 (fatal) events (except death due to progressive disease) must be reported via email within 24 hours. A complete report must be submitted within one business day.
- All other serious adverse events including deaths due to progressive disease must be reported within one business day

Study endpoints that are serious adverse events (e.g. all-cause mortality) must be reported in accordance with the protocol unless there is evidence suggesting a causal relationship between the drug and the event (e.g. death from anaphylaxis). In that case, the investigator must immediately report the death to the sponsor.

Events will be submitted to the Center for Cancer Research (CCR) at: [contact]

7.3.2 Annual Reporting of AEs to the Sponsor

7.4 FDA REPORTING CRITERIA

7.4.1 IND Safety Reports to the FDA (Refer to 21 CFR 312.32)

The Sponsor will notify the FDA of any unexpected fatal or life-threatening suspected adverse reactions as soon as possible but no later than 7 calendar days of initial receipt of the information using the MedWatch Form 3500a.

The Sponsor is also responsible for reporting:

- any suspected adverse reaction that is both serious and unexpected;
- any findings from clinical, epidemiological, or pooled analysis of multiple studies or any findings from animal or in vitro testing that suggest a significant risk in humans exposed to the drug;
- clinically important increase in the rate of a serious suspected adverse reaction over that listed in the protocol or investigator brochure;

to the FDA and to all investigators no later than 15 calendar days after determining that the information qualifies for reporting using the MedWatch Form 3500a. If FDA requests any

additional data or information, the sponsor must submit it to the FDA as soon as possible, but no later than 15 calendar days after receiving the request.

7.4.2 FDA Annual Reports (Refer to 21 CFR 312.33)

The study Sponsor will submit a brief report annually of the progress of the trial within 60 days of the anniversary date that the IND went into effect as indicated in 21CFR 312.33, and any associated FDA correspondences regarding the IND annual report.

7.5 DATA AND SAFETY MONITORING PLAN

7.5.1 Principal Investigator/Research Team

The clinical research team will meet on a regular basis, biweekly when patients are being actively treated on the trial to discuss each patient in detail. The PI will meet regularly with participating site investigators during study enrollment and treatment. Decisions about dose level enrollment and dose escalation during the phase I portion will be made based on the toxicity data from prior patients.

All data will be collected in a timely manner, entered into C3D and reviewed by the principal investigator or a lead associate investigator in a timely manner. Adverse events will be reported as required above. Any safety concerns, new information that might affect either the ethical and or scientific conduct of the trial, or protocol deviations will be immediately reported to the IRB using iRIS and to the Sponsor.

The principal investigator will review adverse event and response data on each patient to ensure safety and data accuracy. The principal investigator will personally conduct or supervise the investigation and provide appropriate delegation of responsibilities to other members of the research staff.

7.5.2 Sponsor Monitoring Plan

This trial will be monitored by personnel employed by Harris Technical Services on contract to the NCI, NIH. Monitors are qualified by training and experience to monitor the progress of clinical trials. Personnel monitoring this study will not be affiliated in any way with the trial conduct.

At least 25% of enrolled patients will be randomly selected and monitored at least biannually, based on accrual rate. The patients selected will have 100% source document verification done. Additional monitoring activities will include: adherence to protocol specified study eligibility, treatment plans, data collection for safety and efficacy, reporting and time frames of adverse events to the NCI IRB and FDA, and informed consent requirements. Written reports will be generated in response to the monitoring activities and submitted to the Principal investigator and Clinical Director or Deputy Clinical Director, CCR, NCI.

8 STATISTICAL CONSIDERATIONS

8.1 PHASE I PORTION

The phase I portion of this study will enroll patients in a standard 3 + 3 design as described in Section [Error! Reference source not found.](#). The cohort at the recommended dose or MTD will be expanded to 12 patients, and attempts will be made to enroll at least 6 patients that are ≥ 12 years of age and 6 patients that are < 12 years of age to gain experience with a broad age range of patients.

The maximum number of evaluable patients for this phase is 18 (6 patients at 2 dose levels and 6 to expand MTD to 12).

8.2 PHASE II PORTION

The primary endpoint will be objective response by RECIST criteria v 1.1. The best response of disease to mithramycin will be examined. The following outlines the Simon optimal two stage design that will be used:

	Cumulative Number of Responses	Decision
Stage 1: Enter 9 patients	0	Terminate the trial: agent ineffective
	1 or more	Inconclusive result, continue trial (proceed to Stage 2)
Stage 2: Enter 15 additional patients	2 or fewer	Terminate the trial: agent ineffective
	3 or more	Terminate the trial: agent effective

We will consider mithramycin not of sufficient interest for further evaluation in a disease category if the true response rate is 5% ($p_0=0.05$) and of sufficient activity if the true response rate is 25% ($p_1=0.25$). As summarized in the above table, with $\alpha=0.10$ (10% probability of accepting an ineffective treatment) and $\beta=0.10$ (10% probability of rejecting an effective treatment), the study will initially enroll 9 patients and if 0 of 9 have a response, then no further patients will be enrolled. If 1 or more respond, accrual will continue until a total of 24 evaluable patients have been enrolled. After 24 patients have been enrolled and evaluated, 1-2 with a response will be considered insufficient while if 3 or more respond in 24 patients, this will be considered sufficient activity for further investigation. Under the null hypothesis, the probability of early termination is 63%.

The two patients that were enrolled in the 25 mcg/kg dose of the Phase II portion will be evaluated for response but not be counted as evaluable for the design above, as they received mithramycin at a higher single dose (25 mcg/kg) than the new phase II dose (17.5 mcg/dose) determined with amendment B. The accrual ceiling will be increased by two patients to allow for these non-evaluable patients.

If the pediatric phase II dose of mithramycin determined on this trial differs from the adult phase II dose, the protocol will be amended to address accrual and response rate to mithramycin in children in a separate stratum.

8.2.1 Methods of Analysis

Patients who are considered evaluable for response will be included in an analysis of time to progression. Time to progression will be estimated using the product-limit method of Kaplan and Meier. The probability of progression free survival at 6 months will be summarized. Response rates will be calculated as the percent of patients whose best response is a CR or PR, and the fraction of responses obtained will have a 95% confidence interval, which takes into consideration the two-stage nature of the design (50). Toxicity information recorded will include the type,

severity, time of onset, time of resolution, and the probable association with the study regimen. Tables will be constructed to summarize the observed incidence by severity and type of toxicity.

Time to progression will be taken as the number of days from enrollment until: (1) disease progression; (2) death because of treatment complications; (3) resection of measurable tumor; or (4) last patient follow-up whichever is first. Patients will be considered to have experienced a progression event if (1) or (2) occurs. Otherwise, the patient will be considered censored for time to progression.

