2.2 SCREENING EVALUATION

2.2.1 General

Pre-treatment blood test should be performed within 7 days and imaging studies within 2 weeks prior to enrollment on the trial unless otherwise stated. The evaluations required prior to starting treatment are listed in table form in Appendix 3 Study Calendar.

HISTORY AND PHYSICAL EXAMINATION: including documentation of height and weight (average of 3 measurements on the same day), measurable disease, vital signs (blood pressure, heart rate, respiratory rate, temperature), performance status, history of bleeding disorder, HIV, HBV, HCV, and signs and symptoms within one week of enrollment.

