c. Evaluation of Best Overall Response

The best overall response is the best response recorded from the start of the treatment until disease progression/recurrence (taking as reference for progressive disease the smallest measurements recorded since the treatment started). The patient's best

response assignment will depend on the achievement of both measurement and confirmation criteria.

Target Lesions	Non-Target Lesions	New Lesions	Overall Response	Best Overall Response when Confirmation is Required*
CR	CR	No	CR	≥ 4 wks. Confirmation**
CR	Non-CR Non-PD	No	PR	≥ 4 wks. Confirmation**
CR	Not evaluated	No	PR	
PR	Non-CR Non-PD Not evaluated	No	PR	
SD	Non-CR Non-PD Not evaluated	No	SD	Documented at least once ≥ 4 wks. from baseline**
PD	Any	Yes or No	PD	No prior SD, PR or CR
Any	PD***	Yes or No	PD	
Any	Any	Yes	PD	

*See RECIST 1.1 manuscript for further details on what is evidence of a new lesion.
**Only for non-randomized trials with response as primary endpoint.
***In exceptional circumstances, unequivocal progression in non-target lesions may be accepted as disease progression

- d. Patients with a global deterioration of health status requiring discontinuation of treatment without objective evidence of disease progression at that time should be reported as “*symptomatic deterioration*.” Every effort should be made to document the objective progression even after discontinuation of treatment.
- e. In some circumstances, it may be difficult to distinguish residual disease from normal tissue. When the evaluation of complete response depends on this determination, it is recommended that the residual lesions be investigated (fine needle aspirate/biopsy) before confirming the complete response status.

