8.3 EVALUATION OF RESPONSE

Any patient who is enrolled and receives at least one dose of mithramycin will be considered evaluable for response provided: (1) the patient demonstrates progressive disease or death while on protocol therapy; (2) the patient is observed on protocol therapy for at least one cycle and the tumor is not removed surgically prior to the time complete response or partial response is confirmed; or (3) the patient demonstrates a complete or partial response as confirmed according to protocol criteria. Patients who electively terminate therapy before receiving all 7 doses of mithramycin during the first treatment cycle and do not expire within 28 days from start of treatment will be replaced. Patients who demonstrate a complete or partial response will be considered to have experienced a response. The evaluation period for determination of the best response will be 6 treatment cycles. All other patients will be considered non-responders.

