11.7 APPENDIX 7: STUDIES TO BE PERFORMED ON TUMOR TISSUE

Archival tumor tissue

a) Archival paraffin embedded tumor tissue for confirmation of EWS/FLI1 fusion transcript to determine eligibility for phase II portion of trial, and for evaluation of NR0B1 expression in patients with Ewing sarcoma

Archival paraffin embedded tissue, or if paraffin embedded tissue is not available, 5 consecutive unstained slides, should be sent via express carrier to:

[name]
NCI, POB
[name]
[name]
[name]
[contact]

Please notify [name] by e-mail ([contact]) prior to shipment.

[name] will submit these samples to the Laboratory of Pathology for testing.

Tumor tissue from Mandatory tumor biopsies for NR0B1 expression and gene signature (Phase II)

In patients with Ewing sarcoma and EWS-FLI1 fusion transcript \geq 18 years old, who have disease amenable to percutaneous biopsy, and who meet other eligibility criteria for biopsy, a biopsy will be obtained prior to treatment and at steady state on treatment during cycle 1. Patients who meet these criteria will have to agree to the biopsies in order to be able to participate in the trial.

Tumor Biopsies

Willingness to undergo tumor biopsies is required for patients with disease amenable to percutaneous biopsy on this protocol because modulation of molecular targets in tumor biopsies after drug treatment is an important objective of this study.

Baseline biopsies will be performed following patient enrolling on study. If an initial attempt at percutaneous biopsy is unsuccessful, the patient will be given an option to proceed with a repeated attempt at percutaneous biopsy. A separate consent form must be signed for each biopsy procedure, so patients may choose not to undergo subsequent biopsies. If the baseline biopsy is unsuccessful or the patient refuses to undergo subsequent biopsies, no further biopsies will be performed, but the patient will remain on study, receive study medication, and other correlative studies will be performed. Similarly, patients who miss the first dose of drug will not subsequently be biopsied, but will remain on study.

Timing of tumor biopsies

For NR0B1 expression and gene expression signature tumor one tumor biopsy each will be obtained prior to treatment, and day +4 (+/- 1 day) during cycle 1 at steady state on treatment with mithramycin.

Biopsy procedure

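### Time to progression is counted from enrollment in a set that requires a first dose, so each analysed patient's time includes an enrollment-to-dose interval that is event-free in practice (minor)

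*Combined protocol and SAP*

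**What the plan says.** Section 8.2.1 sets the time origin: "Time to progression will be taken as the number of days from enrollment until" progression, death from treatment complications, resection of measurable tumor or last follow-up, whichever comes first. Only the first two are events. The analysis uses Kaplan-Meier, and a 6-month progression-free probability is also to be reported.

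The same section fixes the analysis set: "Patients who are considered evaluable for response will be included in an analysis of time to progression". Section 8.3 defines that set: "Any patient who is enrolled and receives at least one dose of mithramycin will be considered evaluable for response provided" one of three further conditions is met. The first of these is that "the patient demonstrates progressive disease or death while on protocol therapy".

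Three passages bear on the time between enrollment and first dose:

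- Section 2.2.1 asks for "imaging studies within 2 weeks prior to enrollment on the trial unless otherwise stated".
- Section 6.2.9 asks for baseline evaluations as near as possible to the start of treatment and "never more than 4 weeks before the beginning of the treatment".
- Appendix 7 (11.7), on the mandatory biopsies in eligible adults, says "Baseline biopsies will be performed following patient enrolling on study".

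Section 1.1.2 lists TTP as a secondary objective, to be defined only preliminarily.

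**The concern.** The time origin and the analysis set do not match. To be analysed, a patient must have reached a first dose, yet the clock has been running since enrollment. A patient who progresses, dies or withdraws before dosing is not in the analysis, and a patient who gets through the wait has it added to TTP. This is guaranteed event-free time (immortal time), and the error runs only in the drug's favour.

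A single-arm trial has no control arm in which the same shift would cancel. The wait also reflects logistics such as biopsy scheduling, so it can differ between patients for reasons unrelated to the drug. At stake are the reported median TTP and the 6-month probability, which readers may set beside figures from other studies that start the clock differently.

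**Working it through.** The documents give no median, event count or null value for TTP, so there is no stated figure to reproduce.

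**Step 1. Decomposition.** Let G be a patient's days from enrollment to first dose. For a patient in the analysis set:

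reported TTP = G + (time from first dose to the end point)

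G is event-free in practice. A death from treatment complications requires treatment, and restaging is scheduled only after even cycles (3.5.1.5). This is not a written rule, because 8.2.1 does not say how progression before the first dose is handled in a patient who is then dosed.

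**Step 2. How large G can be.** Let d be the days from baseline scan to enrollment. Section 2.2.1 gives 0 ≤ d ≤ 14, and 6.2.9 gives d + G ≤ 28. Hence the maximum G is 28 − d:

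- d = 0: 28 days
- d = 7: 21 days
- d = 14: 14 days

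The minimum is 0. These are ceilings, not expected values.

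**Step 3. Median.** If all patients share a gap g, the median rises by exactly g. If gaps vary, it rises by roughly the typical gap. The medians below are assumptions.

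| Assumed median from first dose | g = 7 days | g = 14 days | g = 28 days |
|---|---|---|---|
| 2 months (60.9 days) | 67.9 (+11%) | 74.9 (+23%) | 88.9 (+46%) |
| 3 months (91.3 days) | 98.3 (+8%) | 105.3 (+15%) | 119.3 (+31%) |
| 6 months (182.6 days) | 189.6 (+4%) | 196.6 (+8%) | 210.6 (+15%) |

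**Step 4. 6-month probability if progression were observed continuously.** With T = 182.6 days and exponential times with median m from first dose, the enrollment clock reports

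S(T − g) = exp(−ln 2 × (T − g) / m)

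Example with m = 60.9 and g = 14: exp(−0.693 × 168.6 / 60.9) = 14.7%, against 12.5% with g = 0.

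| Assumed median | g = 0 | g = 7 | g = 14 | g = 28 |
|---|---|---|---|---|
| 2 months | 12.5% | 13.5% | 14.7% | 17.2% |
| 3 months | 25.0% | 26.4% | 27.8% | 30.9% |
| 4 months | 35.4% | 36.8% | 38.3% | 41.5% |
| 6 months | 50.0% | 51.3% | 52.7% | 55.6% |

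**Step 5. 6-month probability on the protocol's scan schedule.** With 28-day cycles, scans after even cycles fall nominally on days 56, 112, 168 and 224 from first dose. The scan that matters is the one after cycle 6:

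- g = 14: 168 + 14 = day 182 from enrollment, before 182.6. Status at 6 months is unchanged.
- g = 15: 168 + 15 = day 183, after 182.6. A patient whose progression is first seen on that scan now counts as progression-free at 6 months.

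For scan-detected progression on the nominal schedule, the smooth shifts in the 7- and 14-day columns of step 4 therefore do not appear. They can appear with clinically detected progression or off-schedule scans. Section 7.2.4 tolerates evaluations 7 days off schedule. A scan on day 175 crosses the landmark with an 8-day gap, since 175 + 8 = 183.

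**Step 6. Scale against sampling error.** With 24 patients and no censoring, the binomial standard error is √(0.125 × 0.875 / 24) = 6.8 points at 12.5% and √(0.25 × 0.75 / 24) = 8.8 points at 25%. The 28-day shifts in step 4 are 4.7 and 5.9 points.

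**The case against.** The strongest reply is that the effect may be negligible. No passage gives an actual delay, and 6.2.9 asks for baseline evaluations as close to treatment as possible. The biopsy is the main stated reason for a wait, and it applies only to adults with suitable lesions. The study calendar (Appendix 3) lists it in the screening/baseline column, although Appendix 7 puts it after enrollment. TTP carries no test, threshold or decision, and even the largest shift in step 6 is below one standard error. Best response runs from treatment start ("The best overall response is the best response recorded from the start of the treatment until disease progression/recurrence"), but that describes an observation window for a proportion, so it shows little about the right origin for a survival clock.

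All of this stands, and it limits the size of the problem. It does not remove the mismatch, because no other passage brings the origin and the analysis set into line. Sampling error does not excuse a bias of known direction that a wording change would remove.

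A reader might infer something stronger: that the protocol allows a 28-day gap, that every TTP value is inflated, and that the 6-month figure is materially wrong. The documents do not support that:

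- Twenty-eight days is an inferred ceiling. It needs the scan on the enrollment day and full use of the 4-week limit. Part of the registration section (2.3) was not available for this review, so a start-of-treatment window there cannot be excluded.
- A patient dosed on the day of enrollment gains nothing.
- The smooth 6-month shifts assume continuous observation and medians that the documents do not give.

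A longer wait in biopsied adults than in children is plausible, but no passage quantifies it and no comparison by age is planned.

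**Conclusion.** The point holds as a minor inconsistency. The TTP clock starts at enrollment while the analysis set is conditioned on a later event, the first dose, and the resulting bias is upward.

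The median is overstated by roughly the typical enrollment-to-dose interval. That interval is unknown, may be zero, and has an implied ceiling of 14 to 28 days depending on the scan date. Some gap is likely in biopsied adults. On the nominal scan schedule, gaps up to 14 days leave scan-detected 6-month status unchanged. Under continuous observation with assumed exponential medians of 2 to 6 months, a 28-day gap in every patient would add about 5 to 6 percentage points, which is an outer bound for that range of medians.

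The conclusion on direction rests on the wait being event-free in practice. The primary response rate and the two-stage decision rule do not use this clock and are unaffected.

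**What to change.** In section 8.2.1, replace enrollment with the first dose of mithramycin as the time origin for TTP and for the 6-month probability. Time zero then matches the dosed analysis set, and the added gap becomes zero for every patient. It would also help to report the distribution of the enrollment-to-first-dose interval and the number of patients enrolled but never dosed.

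Keeping enrollment as the origin and analysing all enrolled patients would also remove the mismatch. It answers a different question, however, and needs progression follow-up in undosed patients, whereas the restaging schedule is tied to treatment cycles.

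The cost is a wording change. The pharmacokinetic worksheet (Appendix 4) already records the date and start time of the day 1 infusion, and neither the sample size nor the design changes. The only downside is that reported TTP becomes slightly shorter.
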